6.3.2	Haemodialysis visits during study observation period	24
6.3.3	Week 2, Week 4 and Week 6 clinic visits	24
6.3.4	Week 8 visit (end of study)	25
7.	Statistical methods	25
7.1	Statistical design and model	25
7.2	Null and alternative hypotheses	26
7.3	Planned analyses	26
7.3.1	Primary analyses	26
7.3.2	Secondary analyses	26
7.3.3	Safety analyses	26
7.3.4	Interim analyses	26
7.3.5	Health economic analyses	27
7.4	Handling of missing data	27
7.5.	Randomisation	27
7.6	Determination of sample size	27
8.	Informed consent, data quality and storage	27
8.1	Study approval, patient information and informed consent	27

8.2 Data quality assurance	27
8.3 Records	27
8.3.1 Source documents	27
8.3.2 Direct access to source data and documents	28
8.3.3 Storage of records	28
8.4 Statement of confidentiality	28
8.5 Completion of trial	28
8.6 Protocol violations	28
8.7 Compensation available in the event of study-related injury	28
9. References	29
10. Appendices	30
Appendix 10.1 Cointerventions protocol	30

Protocol Summary

Product	Machine learning algorithm to assess fluid status
www.clinicaltrials.gov identifier	
Protocol title	Pilot-scale, single-arm, observational study to assess the utility of a machine learning algorithm to assess fluid status in haemodialysis patients
Principal investigator	[name], Beaumont Hospital, [name]
Number of study sites	1: Beaumont Hospital dialysis centre.
Study objectives	To determine the validity and reproducibility of a machine learning algorithm that assesses fluid status compared with bioimpedance and clinical dry weight estimation in ambulatory haemodialysis patients.
Methodology	Open, prospective, single-arm observational
Number of subjects	Total treated: 20
Diagnosis	End Stage Kidney Disease requiring regular ongoing ambulatory haemodialysis
Main criteria for inclusion	Age ≥ 18 years, demonstrated understanding of study processes, written informed consent
Test product/intervention	Fluid status estimation model
Comparator product/intervention	None
Duration of observation	8 weeks/patient
Primary endpoint(s)	Fluid status predicted by machine learning algorithm compared to bioimpedance data
Secondary endpoint(s)	Symptoms, adverse events.
Interim analysis	None planned

Statistical methods	Descriptive tables or figures will be prepared. Within-patient comparison of fluid status data as determined by different methodologies.
---------------------	---

Flow charts

Flow chart 1 Assessments during observation period

	study observation period (8 weeks)			
	Baseline visit	At each dialysis session	Week 2 Week 4 Week 6	Week 8 (end)
Informed consent	X			
Demographic data (include dialysis & medicines history)	X			
Vital signs, body weight, routine hemodialysis measurements in-clinic ^A	X	X	X	X
Assess fluid status with bioimpedance ^B	X		X	X
Estimate fluid status using machine learning algorithm ^C	X	X	X	X
Record symptoms related to fluid status ^D	X		X	X
Record adverse events ^E		X	X	X
End of study				X

^A Routine measurements (at each hemodialysis session) include total fluid removal, interdialytic weight gain (IDWG), proportion of haemodialysis sessions in which IDWG is $\leq 4\%$, pre-dialysis and post-dialysis weight, pre-dialysis, intradialytic and post dialysis BP and pulse rate.

^B Fluid status will be assessed by bioimpedance measurements immediately before start of haemodialysis.

^C The machine learning model is a software program which examines the demographic data, recent vital signs, body weight and hemodialysis measures to predict a patient's fluid status.

^D Symptoms related to fluid status will be recorded before haemodialysis.

^E For example, requirement for nursing intervention such as stopping dialysis or administering fluid bolus. Adverse events include, but are not limited to muscle cramps, symptomatic hypotension, access-related complications, hypertension-related symptoms, congestive heart failure, pulmonary edema, requirement for additional unscheduled dialysis, or need for hospitalisation and changes in number and type(s) of BP medications.

List of figures and tables

Figure 1.2: 1 Diagram of machine learning model

Figure 3.1: 1 Diagram of study design

List of abbreviations and terms

BP	blood pressure
BVM	blood volume monitoring
CV	cardiovascular
DTIF	Disruptive Technologies Innovation Fund
ECW	extracellular water
HOPE	Haemodialysis Outcomes & Patient Empowerment
IDWG	interdialytic weight gain (fluid weight gain between dialysis sessions)
L	litre
OH	overhydration
PND	paroxysmal nocturnal dyspnea

1. Introduction

1.1 Medical background

End stage kidney disease is defined by kidney failure severe enough to require some form of renal replacement therapy. This replacement has three forms, kidney transplant, haemodialysis and peritoneal dialysis. Haemodialysis is the most common form of replacement therapy and usually entails three sessions of dialysis per week on alternate days starting either on Monday or Tuesday. The period between dialysis sessions is known as the interdialytic period and as dialysis is delivered on alternate days there is one interdialytic period per week that is longer than the other. In order to maintain extracellular fluid balance and to prevent high blood pressure, haemodialysis sessions focus on removing the fluid that was gained between dialysis sessions.

Haemodialysis patients experience high rates of mortality, driven largely by an exceptionally high rate of cardiovascular (CV)-related mortality, which exceeds that of the general population by 10-to 20-fold [1, 2]. High levels of both interdialytic weight gain and rate of fluid removal during dialysis have been linked with increased mortality, particularly during the longer interdialytic period [1]. It is postulated that the haemodynamic effects of high fluid removal rates during dialysis may result in cardiovascular morbidity and mortality. Similarly, volume depletion induced by excessive ultrafiltration is associated with myocardial stunning, cerebrovascular events and mortality [3,4].

However, at present no method exists that can consistently refine volume status and provide patients with feedback to allow adjustments to their fluid intake. Current standards used to assess volume are either poorly predictive of fluid status, cumbersome to use, or lack an adequate patient interface [1].

The advent of the electronic health record has given us access to large quantities of patient data, which are ideal for data analytics and machine learning [2, 3]. Dialysis datasets contain large amounts of heterogeneous clinical data collected at thrice weekly intervals, creating the ideal environment to form individualised predictive algorithms. Machine learning methods have been applied to guide complex decision making within the dialysis unit [4, 5, 6], and in the prediction of

volume-related adverse events, such as intradialytic hypotension [7] and dry weight.

Volume assessment is arguably an ideal task for machine learning. Each method regularly used to assess volume, such as blood pressure (BP), and the relative blood volume slope, has partial predictive power in assessing fluid status [8,9]. Machine learning has the ability to synthesise multiple variables with partial predictive power in order to improve prediction accuracy. Several prototype models for dry weight assessment exist [10, 11, 12] but to date, only one of these models has been assessed in a prospective clinical trial [10].

We have created a prototype machine learning model based upon the data of 100,000 dialysis patients collected over 1 year from an anonymised database provided by Fresenius.

This study will evaluate if this machine-learning model for assessing fluid status is acceptable and usable for managing fluid volume in haemodialysis patients, while also assessing validity and reproducibility against validated measurements.

As the machine learning model for assessing fluid status was trained and tested on retrospective data, there is sufficient justification in testing the performance plus acceptability and usability of the model in a controlled observational setting in a prospective study. To date, this approach has not been explored in haemodialysis patients.

[figure not shown]
This is a pilot-scale study to assess if this approach has merit and could be tested and developed further.

1.2 Product profile

The machine learning model is a software program designed to assess fluid status in patients with end stage renal disease. It was developed on a large retrospective global dataset of anonymised dialysis patient data. The machine-learning model software program was designed to predict fluid status using patient demographic information and data from their recent dialysis sessions. This machine-learning model software program was trained using standard algorithm approaches on the global dialysis dataset.

In this prospective pilot study, the machine-learning model will be run every two weeks for each patient on their recently recorded information to estimate their fluid status. The inputs for the machine-learning model include demographic data (include dialysis & medicines history), vital signs, body weight and routine hemodialysis measurements in-clinic for the patient. The output from the machine-learning model is the predicted fluid status individualised for the patient. An illustration of the inputs and output for the machine-learning model is shown in Figure 1.2: 1 below.

Figure 1.2: 1 Diagram of machine learning model

The study team will complete all tasks required to run and assess the machine-learning model. (No action is required by the patient in running or assessing the machine-learning model.) The machine-learning predicted fluid status will not be used to adjust the patient's treatment regimen and the patient will not be informed of the machine-learning predicted fluid status.

2. Rationale, objectives and benefit-risk assessment

2.1 Rationale for performing the study

This study will evaluate if a machine learning model to estimate fluid status is acceptable and usable for managing fluid volume in haemodialysis patients, and will also evaluate validity and reproducibility against validated measurements.

This is a pilot-scale study to assess if this approach has merit and could be tested and developed further.

As the machine-learning model for estimating fluid status was trained and tested on retrospective data, there is sufficient justification in testing the performance plus acceptability and usability of the model in a controlled observational setting.

2.2 Study objectives

The objective of this pilot-scale study is to assess how the machine learning estimation model functions when used in a range of haemodialysis patients of varying age, gender, body habitus and volume status.

The primary objective is to determine the validity and reproducibility of the machine learning estimation model in haemodialysis patients. (The goal is to determine if the machine learning estimation model can provide actionable insights to better manage fluid overload in the interdialytic period.)

Haemodialysis parameters will be assessed as usual during the study and will include:

- total fluid removal (each haemodialysis session)
- interdialytic weight gain (IDWG)
- proportion of haemodialysis sessions in which IDWG is $\leq 4\%$.
- pre-dialysis weight
- post-dialysis weight
- Pre-, intra- and post-dialysis BP
- pulse rate
- dialysis access pressures
- dialysis flow rate and blood flow rate
- dialysis temperature
- routine haemodialysis monthly haematology (e.g. haemoglobin) and blood chemistry [renal profile (e.g. sodium, potassium), bone profile (e.g. calcium, phosphate)] data
- number and type(s) of BP medications
- requirement for nursing interventions (e.g. stopping dialysis or administering fluid bolus)
- adverse events requiring or prolonging hospitalisation

- requirement for additional unscheduled dialysis

Fluid status estimated by the machine learning estimation model will be compared with bioimpedance findings.

Patient-reported symptoms related to haemodialysis and their underlying medical condition will be recorded before haemodialysis. Adverse events and unscheduled interventions will be recorded. The effect of symptoms, adverse events and interventions on the performance of the model will be evaluated.

2.3 Benefit-risk assessment

This study is designed to contribute to the development of a multivariate algorithm to help haemodialysis patients monitor and manage their fluid intake. The machine learning estimation model will be used to estimate fluid removal requirements during multiple haemodialysis sessions. The estimated values will be compared with actual values to assess the validity of the machine learning estimation model.

The machine learning estimation model will not be used to adjust the patient's haemodialysis treatment regimen during this study. The machine learning estimation model does not provide feedback to the patient. It is not expected that the study or the machine learning estimation model will create any additional risks for the haemodialysis patients in this study.

All patients will receive optimal haemodialysis during the study. In addition, the on-call nephrology registrar at Beaumont hospital will be available to handle any medical enquiries from patients enrolled in the study.

[figure not shown]
3. Description of design and study population

3.1 Overall design and plan

Prospective, open-label run-in observation period (8 weeks). (See Figure 3.1: 1 for diagram of design.)

The study will not make any changes to the usual haemodialysis schedule for the patients.

Figure 3.1: 1 Diagram of study design

3.1.1 Administrative structure of study

This is a single centre study at the Beaumont Hospital, a tertiary care centre for nephrology in Dublin, Ireland.

Fresenius supplied an anonymized dataset which was used to create the machine learning model to estimate fluid status which is being evaluated in this study. Fresenius did not have any input into the design of this study.

The study is being conducted as part of the Haemodialysis Outcomes & Patient Empowerment (HOPE) project supported by the Disruptive Technology Innovation Fund of Ireland (DTIF). The HOPE project is a collaboration between the Royal College of Surgeons in Ireland, Beaumont Hospital, patientMpower Ltd., [name] and Sixty (registered as Design to Value Ltd.), [name]. The objective of HOPE is to develop artificial intelligence-enabled software to improve determination and maintenance of fluid balance in haemodialysis patients with a long-term goal of increasing the proportion of patients receiving dialysis at home. This study is a

collaboration between all partners in HOPE and the data and outcomes will be shared with all partners. The study is funded by the DTIF.

The protocol was designed by [name] [name] (Principal Investigator), [name] (both of Beaumont Hospital, Dublin 9, Ireland), [name], St. James' Hospital, [name] and patientMpower Ltd., [name].

The study sponsor is the Royal College of Surgeons in Ireland, [name].

patientMpower will be the Data Processor (on behalf of the HOPE project partners) for data collected in this study.

3.2 Discussion of study design, including choice of control group

This is a pilot-scale, prospective, open-label, single-arm observational study.

All patients will be allocated to the same observation sequence.

Patients will follow their usual haemodialysis regimen throughout the study.

Clinical assessments (e.g. IDWG, BP, pulse rate, ultrafiltration volume, symptoms) will be assessed at each dialysis visit.

The study design will allow assessment of the validity and reproducibility of data provided by the machine learning fluid status estimation model in haemodialysis patients. These data will be compared against other validated methods of volume assessment (haemodialysis machine and bioimpedance data) and with observed symptoms in patients across a range of age, genders and volume status.

The study will also allow evaluation of the utility and acceptability of the machine learning fluid status estimation model in a haemodialysis patient population. This will be assessed from the healthcare professional perspective.

3.3 Selection of study population

3.3.1 Main diagnosis for study entry

Require maintenance haemodialysis in an ambulatory care setting.

Patients with a range of baseline fluid status will be considered for enrollment.

3.3.2 Inclusion criteria

Aged at least 18 years

Demonstrates understanding of the study requirements.

Willing to give written informed consent.

3.3.3 Exclusion criteria

Conditions precluding accurate use of bioimpedance (e.g. limb amputations, severe malnourishment, pregnancy, cardiac resynchronisation devices, pacemakers).

Significant confusion or any concomitant medical condition, which would limit the ability of the patient to record symptoms or other parameters.

3.3.4 Removal of patients from therapy or assessments

3.3.4.1 Removal of individual patients

Patients are free to withdraw from the study at any time without any impact on their ongoing medical care.

The investigator may withdraw a patient from the study at any time if they believe that further participation in the study is not in the best interests of the patients.

3.3.4.2 Discontinuation of the trial

The study may be terminated early if recruitment is significantly behind schedule or if for any other reason, it is unlikely that the study can be completed.

4. Study observational intervention

All patients will continue to receive their usual haemodialysis regimen throughout the study as prescribed by their healthcare professionals.

4.1 Observational intervention to be assessed

4.1.1 Identity of observational intervention and comparator(s)

The machine learning estimation model is a software program to assess fluid level that was developed on a large retrospective dataset of anonymised dialysis patient data. The machine-learning model processes recent information for the dialysis session and the patient to predict their fluid status. The recent information includes demographic data (including dialysis & medicines history), vital signs, body weight and their routine hemodialysis measurements in-clinic. The patient will not be involved in running or assessing the machine-learning model software program. The machine-learning model predicted fluid status will not be used to assess the patient's dialysis regimen and no information on the machine-learning model predicted fluid status will be provided to the patient.

There is no comparator intervention.

4.1.2 Method of assigning patients to observational groups

All patients who give informed consent and enter the study will be allocated to the same observation sequence.

4.1.3 Blinding and procedures for unblinding

The study is open-label.

4.2 Concomitant therapy, restrictions and rescue treatment

4.2.1 Rescue medication, emergency procedures and other treatment

If any patient or their healthcare professional has a concern the renal registrar on call at Beaumont Hospital will respond to calls out of hours and at weekends.

Any exacerbations of the patient's underlying medical condition(s) should be treated according to standard procedures.

Any other adverse events should be treated according to standard procedures.

4.2.2 Restrictions

There are no restrictions on concomitant treatment. All concomitant treatments as prescribed by the patients' healthcare professionals are allowed. Patients will continue to take all medicines and other treatments as prescribed by their healthcare professionals. As per the co-interventions protocol (Appendix 10.1), all nephrologists working at Beaumont Hospital will be asked not to alter the patients' usual fluid balance management during the study.

The study does not mandate any additional restrictions on diet or life-style. Patients will continue to follow all instructions on diet, exercise and lifestyle as directed by their healthcare professionals.

4.3 Treatment adherence

Patients will be asked to follow all study-specific instructions as directed by their healthcare professionals.

5 Variables and their assessment

5.1 Efficacy

5.1.1 Efficacy endpoints

5.1.1.1 Primary endpoint

The primary endpoint will be to determine the validity and reproducibility of the machine learning model to estimate dry weight in assessing fluid removal requirements in haemodialysis patients. This will be evaluated by comparing validated monitoring techniques such as bioimpedance.

The primary endpoint variables include:

- volume status as measured by bioimpedance pre-dialysis.

- volume overload as defined by bioimpedance: overhydration (OH)/extracellular water (ECW) > 15% (corresponding to 2.5L)
- normohydration defined as: ECW -7 to + 7% (corresponding to -1.1L to + 1.1L)

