5.1.2 Assessment of efficacy

The primary and secondary endpoint data will be listed and tabulated or displayed graphically.

The primary endpoint will be to evaluate the validity and reproducibility of the machine learning algorithm in estimating fluid status when compared to bioimpedance data. The primary endpoint will be assessed by comparison of the fluid status output of the algorithm versus the fluid status determined by bioimpedance.

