5.4 Appropriateness of measurements

The primary efficacy endpoint variables are measurements which are important and accepted measures of fluid status and renal function in haemodialysis patients.

6 Investigational plan

Patients who participate in the study will follow their usual haemodialysis regimen for approximately eight weeks. The machine learning estimation model will be used to estimate fluid status of patients during the study. In addition to usual care, participating patients will have fluid status measured by bioimpedance on five occasions.

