6.1 Visit schedule

The total observation period will be approximately eight weeks. It is anticipated that patients will attend the clinic for haemodialysis three times per week on average. No additional patient visits are required for this study.

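### Reproducibility is named in the primary endpoint, but the planned comparison addresses agreement and no repeat reading under unchanged fluid status is described

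*Protocol*

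**What the plan says.** The primary objective (section 2.2) is the validity and reproducibility of the model. Section 5.1.1.1 repeats this as the endpoint: "The primary endpoint will be to determine the validity and reproducibility of the machine learning model to estimate dry weight". Section 3.2 says the design will permit both to be assessed. Reproducibility is not defined in any of these places.

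Section 5.1.2 describes the assessment: "The primary endpoint will be assessed by comparison of the fluid status output of the algorithm versus the fluid status determined by bioimpedance". Section 7.3.1 adds haemodialysis machine data to that comparison.

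On the schedule, section 6 says that "participating patients will have fluid status measured by bioimpedance on five occasions". Sections 6.3.1, 6.3.3 and 6.3.4 place these at baseline and weeks 2, 4, 6 and 8. Flow chart 1, note B, fixes the timing: "Fluid status will be assessed by bioimpedance measurements immediately before start of haemodialysis". The number of readings per occasion is not stated, and no repeat is described.

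Model frequency is given in two ways. Section 1.2 says "the machine-learning model will be run every two weeks for each patient". In Flow chart 1, the row "Estimate fluid status using machine learning algorithm ^C" is marked in every column, including the one for each dialysis session.

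Section 4.2.2 says that "all nephrologists working at Beaumont Hospital will be asked not to alter the patients' usual fluid balance management during the study". That concerns management. Nothing in the protocol holds a patient's actual fluid status constant.

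**The concern.** Reproducibility asks how much a method's result varies when the quantity measured has not changed. Agreement asks how close two methods are on the same occasion. The protocol promises both and describes a comparison that delivers the second.

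Fluid status can differ between occasions. Section 1.1 explains that patients gain fluid between sessions and that one gap each week is longer than the others. The study visits are not tied to a weekday or a gap length. A change in model output from one visit to the next is therefore a mixture of real change and model error. Rerunning a fixed program on identical inputs would test only the software.

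At stake is one named component of the primary endpoint. It may go unreported, or be reported under a label that the data support only with untested assumptions. An analysis plan could name a statistic, but it cannot add a same-state repeat to the visit schedule.

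**Working it through.** The protocol gives no figure for reproducibility, and section 7.6 says the sample size of 20 was arbitrary, so there is no stated result to reproduce. Every SD below except the confidence limits in step 4 is an assumed value for illustration.

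**1. Planned data.** Bioimpedance occasions: 1 + 3 + 1 = 5, which matches section 6. Pairs: 20 × 5 = 100. Within-patient degrees of freedom: 20 × (5 − 1) = 80. Section 6.1 says that "patients will attend the clinic for haemodialysis three times per week on average". If the flow chart governs, there are about 3 × 8 = 24 model runs per patient instead of 5.

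**2. One method's series cannot tell error from change.** The within-patient SD of model output is √(s_T² + s_M²), where s_T is the SD of true fluid status over visits and s_M the SD of model error.

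| s_T (L) | s_M (L) | Within-patient SD (L) |
|---|---|---|
| 0 | 1.0 | 1.0 |
| 0.6 | 0.8 | √(0.36 + 0.64) = 1.0 |
| 0.8 | 0.6 | √(0.64 + 0.36) = 1.0 |
| 0.98 | 0.2 | √(0.96 + 0.04) = 1.0 |

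Four different levels of model error give the same observed SD. Session-level runs meet the same difficulty, since fluid status also changes between sessions.

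**3. The paired series can separate them, under assumptions.** The Grubbs estimator takes model error variance as the within-patient variance of the model minus its within-patient covariance with bioimpedance. In 4,000 simulated trials of 20 patients and 5 visits (bioimpedance error SD 0.5 L), with a common scale and independent errors, it averaged 1.00, 0.64, 0.36 and 0.04 for the four cases, all correct. For the smallest, the 95% range was −0.08 to 0.16.

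With s_T = 0.8 and s_M = 0.6 (true error variance 0.36), breaking an assumption gives:

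- model slope 0.7: (0.49 × 0.64 + 0.36) − 0.7 × 0.64 = 0.23 (simulated 0.22)
- model slope 1.3: (1.69 × 0.64 + 0.36) − 1.3 × 0.64 = 0.61 (simulated 0.61)
- error correlation 0.4: (0.64 + 0.36) − (0.64 + 0.4 × 0.5 × 0.6) = 0.24 (simulated 0.24)

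Two methods without same-state repeats cannot show which case applies.

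**4. What the design does deliver.** If both methods share a scale, true change cancels from model minus bioimpedance, leaving an SD of √(s_M² + s_B²) when errors are independent, where s_B is the SD of bioimpedance error. With s_M = 0.6 and s_B = 0.5 this is √0.61 = 0.78 L, so it is not model error alone. On 80 degrees of freedom the 95% chi-square factors for an SD are 0.866 and 1.183, that is −13% to +18%. Missing patients or visits reduce the degrees of freedom; section 8.5 allows a lower recruitment target and section 7.4 rules out imputation.

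**5. Illustration of the mixing.** With s_M = 0.5 L, the model's repeatability coefficient is 2.77 × 0.5 = 1.39 L. Computed from model output alone with s_T = 0.3, 0.8 or 1.2 L, it would be 2.77 × √(0.25 + s_T²) = 1.62, 2.61 or 3.60 L. The protocol does not prescribe this calculation.

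**The case against.** The best defence is that section 5.1.2 ties reproducibility to the comparison with bioimpedance. Since that comparison is repeated at five visits, stable agreement over visits is a natural reading, and naming the statistic is commonly left to an analysis plan. This is fair as far as it goes, and the fix adopts that reading. What stands against it is that the protocol never says so, and stable agreement is not reproducibility in the usual sense.

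A reader might infer three stronger things that the protocol does not support.

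- That variation between visits is planned to be reported as reproducibility. No section says this; the stated analysis is a within-patient comparison between methods. The 1.62 to 3.60 L figures are therefore not a consequence of following the protocol.
- That each method yields a single reading every two weeks. The two-week spacing is certain only for bioimpedance, because the flow chart marks the model at every session. Single bioimpedance readings are an inference from silence.
- That error and real change can never be separated. They can, if a common scale and independent errors are accepted.

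The proposed SD is itself imperfect, since it includes bioimpedance error. It also needs an output scale that the protocol leaves unclear: section 1.2 speaks of fluid status, section 5.1.1.1 of dry weight.

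**Conclusion.** The point holds in a limited form. The protocol claims a property of the design (section 3.2) and places it in the primary objective and endpoint, but describes only an assessment of agreement and no repeat under unchanged fluid status. Isolating model error would rest on a common scale and independent errors, neither of which this design can test.

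The consequence is modest. The study is a descriptive pilot with no hypotheses, and the model output does not affect treatment. No test or error rate is compromised; what suffers is the meaning of one named part of the primary endpoint. The size of the mixing cannot be stated from the protocol, which gives no SDs. The precision of the replacement measure (80 degrees of freedom, −13% to +18%) assumes 20 patients with all five pairs and roughly normal differences with constant within-patient variance.

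**What to change.** 1. In sections 2.2, 3.2, 5.1.1.1 and 5.1.2, replace 'reproducibility' with 'consistency of agreement with bioimpedance over visits'. Define it as the within-patient SD of model minus bioimpedance across the five visits, and state the common scale.
2. State that this SD also contains bioimpedance error and is not test-retest reproducibility. If this narrower claim is not wanted, remove the word from the primary objective and endpoint.
3. Reconcile the model run frequency between section 1.2 (every two weeks) and Flow chart 1 (each session).
4. If session-level runs are confirmed, an exploratory measure may be added: the within-patient SD of model-implied dry weight over consecutive sessions, split by long or short preceding gap. It needs a stated assumption that dry weight is stable over those sessions, which the protocol does not support with data.

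The cost is protocol wording and a small amount of analysis. Items 1 to 3 need no new visit or measurement; item 4 needs only the preceding gap noted for each session. The downside is a narrower claim than reproducibility.
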